## 7.7. Secondary analyses

### Moderated mediation analysis

[figure not shown]
We will describe health and weight control motivation in the overall sample using mean and standard deviation and report the correlation (Pearson's) between the health and weight control motivation scores and level of education.

If the primary analyses suggest that *level of education* moderates the effect of *labelling* or *proportion* on the *mean ED of foods purchased* (i.e., the *labelling\*level of education* or *proportion\*level of education* interaction is significant), mediation analyses will be performed in order to examine the extent to which 1/ health food choice motive, 2/ weight control food choice motive mediates the effect of *level of education* on the *mean ED*.

Conceptual diagram example (labelling):

Statistical diagram example (labelling):

Conditional indirect effect of *level of education* on the *mean ED* through a mediator (M) =  $a(b_1 + b_2 \text{labelling})$ .

The moderated mediation will be tested by estimating the conditional indirect effect of *level of education* on the *mean ED* through M for *labelling* and *no labelling* conditions (resp. the *default* and *increased proportion* conditions) and testing the conditional indirect effect for those conditions using bias-corrected bootstrap. We will use the PROCESS macro (Model 15) on SAS software that provides asymmetric bias-corrected bootstrap confidence intervals for inference about the conditional indirect effects using 5,000 bootstrap samples [37]. Moderated mediation will be tested by determining whether or not the confidence interval for the difference between conditional indirect effects for *labelling* vs. *no labelling* conditions (resp. the *increased* and *baseline availability* conditions) contains zero.

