## 2. OBJECTIVES, OUTCOMES MEASURES AND HYPOTHESES

OBJECTIVES	OUTCOME MEASURES	HYPOTHESES
Primary objective		

To examine the effectiveness of an information-based intervention (ED labelling) and a structural nutrition intervention (greater proportion of lower ED options) on the ED of virtual online supermarket food purchases; and if this effect is different between participants of lower and higher SEP.	Mean ED (kcal/100g) of foods purchased	SEP will influence the effect of the interventions. In particular, ED labelling will reduce ED of foods purchased to a greater extent in participants of higher vs. lower SEP. Conversely, a greater proportion of lower ED options will decrease ED of food purchases equally among participants of lower and higher SEP.
Secondary objectives  To investigate the psychological processes that explain why an information-based intervention (ED labelling) and a structural nutrition intervention (greater proportion of lower ED options) may have differential effects on ED of food purchases among participants of lower vs. higher SEP.	Health and weight control food choices motives (questionnaire score)	The participants of higher SEP will be more motivated by health and weight control in their food choices than participants of lower SEP, which will moderate the relationship between SEP and the effect of ED labelling on ED of foods purchased.

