## 7. STATISTICAL ANALYSIS

All statistical analyses will be performed using SAS version 9.3 (SAS Institute, Inc., 2012 SAS® 9.3. Cary, NC). The level of significance will be set at  $p < 0.05$  for primary and sensitivity analyses and at  $p < 0.01$  for secondary analyses.

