#### **7.8. Sample size**

##### To observe differences between the intervention groups and interaction with SEP

In a previous study (n=1,088) using the online supermarket platform, two types of nutritional interventions targeting a reduction of saturated fat (SFA) were compared: 1/ altering the default order of products in ascending order of SFA content 2/ offering explicit swaps with lower SFA [28]. This study showed a large main effect (f=0.42) of altering the default order: -4.78% (95%IC: -5.43 to -4.12) of energy from SFA; and a small-to-medium main effect (f=0.12) of offering swaps: -1.48% (95%IC: -2.19 to -0.76) of energy from SFA. Regarding ED reduction, this study showed a small-to-medium main effect (f=0.14) of altering the default order: -5.16 (95%IC: -7.3 to -3.02); and no significant main effect (f=0.04) of offering swaps -1.5 (95% IC: -3.65 to 0.67).

Based on these previous results, we will power our analyses to detect small main effects (f=0.1) of the *labelling* and *increased proportion* interventions. In an ANCOVA including four groups (*control*, *labelling*, *increased proportion*, *increased proportion & labelling*) and one covariate (*level of education*), to detect a main effect of *labelling* or *increased proportion* we will require a sample size of 788 participants (197 per group) for 80% power at  $\alpha = 0.05$  (GPower 3.1).

A sample size of 788 participants will allow to detect small interaction effects (f=0.1) of *labelling* or *increased proportion* with *level of education* in an ANCOVA including four groups (*control*, *labelling*, *increased proportion*, *increased proportion & labelling*) and one covariate (*level of education*) for 80% power at  $\alpha = 0.05$  (GPower 3.1).

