##### To observe a mediated effect of SEP through health and weight control motives

Based on existing literature we hypothesise that the relationship between SEP and food choice motives will be small-to-medium in size [38]. Moreover, in a previous trial we ran using a virtual fast food restaurant ([osf.io/ajcr6](https://osf.io/ajcr6)), we found a small-to-medium correlation between level of education and healthiness motivation ( $r=0.17$ ) as well as small-to-medium correlation between healthiness motivation and kcal ordered ( $r=-0.25$ ). Empirical estimates of sample sizes needed for 0.8 power in mediation analyses indicate that samples of  $\approx 380$  are sufficient to detect mediation through pathways that are small and small-to-moderate in statistical size using bias-corrected bootstrap tests

[39]. Thus, a sample of 788 participants (i.e., 394 per *labelling* or *proportion* condition) allow for adequate power in our planned moderated mediation analysis.

We will recruit a sample of 1,000 participants (= participants who completed the entire study) to account for potential data loss due to incorrect answers, technical problems, failed attention checks, no compliance with the shopping task (up to ~20%) resulting in a minimum sample of 788 participants for our primary analyses.

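### The moderated mediation runs only after a significant education interaction, a precondition that the test does not need and that the Section 7.8 power statement leaves out

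*Combined protocol and SAP*

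**What the plan says.** - **Hypothesis.** Section 2 (secondary objective) expects participants of higher SEP to be more motivated by health and weight control, "which will moderate the relationship between SEP and the effect of ED labelling on ED of foods purchased". Section 1 words the same idea as mediation of the differential labelling effect. Neither makes the test depend on a significance result.
- **Precondition.** Section 7.7 runs the mediation if the primary analyses suggest that education "moderates the effect of *labelling* or *proportion* on the *mean ED of foods purchased", which it defines as either interaction being significant: if the labelling-by-education or proportion-by-education "interaction is significant), mediation analyses will be performed in order to examine the extent to which" each motive mediates the effect of education on mean ED. Means, SDs and the correlations of the motive scores with education are reported in any case.
- **Test.** Section 7.7 defines the conditional indirect effect as a(b1 + b2·labelling). It tests the difference between labelling conditions, which is a × b2, with a bias-corrected bootstrap interval.
- **Levels.** Section 7 sets 0.05 for primary and 0.01 for secondary analyses.
- **Power.** Section 7.8 states that "A sample size of 788 participants will allow to detect small interaction effects (f=0.1) of" either intervention with education, at 80% power. For the mediation it cites a "small-to-medium correlation between level of education and healthiness motivation" (r = 0.17) and a correlation of -0.25 between motivation and kcal ordered. It refers to a 0.8-power benchmark of about 380 participants and concludes that 788 is adequate. The precondition is not mentioned.

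**The concern.** The total education-by-labelling interaction is the motive component (a × b2) plus whatever reaches the outcome by other routes. The precondition asks the noisy sum to be significant before the much more precise component may be examined. If motives are the main route, which is the mechanism the protocol proposes, the sum may be far too small for a test sized at f = 0.1 even when the component is easy to detect. The moderated mediation would then often go untested, and the power stated for it would describe an analysis that is not run. When it is run, the sample has been selected for a large total interaction, which affects any statement about how much of that interaction the motives explain.

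**Working it through.** **1. The plan's own figure.** With noncentrality N·f² = 788 × 0.01 = 7.88 on 1 and 783 df, power at the 5% level is 80.06%. The smallest N is 787, or 788 in four equal groups. The stated 788 is reproduced.

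**2. Inputs.** From Section 7.8: a = 0.17, N = 788, 394 per labelling condition, f = 0.1 for the interaction. Not in the documents, so assumed:
- the change in motive slope under labelling (Δb): 0.25, for example from 0 to -0.25, with 0.50 as an alternative;
- a direct education-by-labelling interaction (c): from 0 up to the value that makes the total f = 0.1.

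**3. Link to f.** With standardised variables and equal arms, the difference in education slope between labelling conditions is a·Δb + c, and f is half of it.
- Motive only: 0.17 × 0.25 = 0.0425, so f = 0.021.
- Slope from 0 to -0.50: 0.17 × 0.50 = 0.085, so f = 0.0425.
- Planned f = 0.1: slope difference 0.20, so c = 0.20 - 0.0425 = 0.1575.

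**4. Precision (slope change 0.25).**
- Total interaction: SE ≈ 2/√788 = 0.071.
- a × b2: SE(a) ≈ √((1 - 0.17²)/788) = 0.035 and SE(b2) ≈ 0.071, so SE ≈ √((0.17 × 0.071)² + (0.25 × 0.035)²) = 0.015.
- In the motive-only case the same true value, 0.0425, is 0.6 SE from zero as a total and 2.8 SE as an index.

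**5. Chances at N = 788.** The precondition was computed by noncentral F and checked with 20,000 simulated trials per scenario. The index was tested by joint significance of a and b2, as a stand-in for the bootstrap.

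| Scenario | Labelling precondition met | Index significant, 5% / 1% | Both, 5% / 1% |
|---|---|---|---|
| Slope change 0.25, c = 0 | 9% | 93% / 80% | 8–9% / 7% |
| Slope 0 to -0.50, c = 0 | 21–22% | >99% / 99% | 22% / 22% |
| Slope change 0.25, total f = 0.1 | 80% | 93% / 80% | 74–75% / 64–65% |

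With c = 0.05 or 0.10 and a slope change of 0.25, the precondition is met in 25% or 52%. At a slope difference of 0.0425, 80% power for the total interaction would need about 17,400 participants.

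**6. The either/or rule.** If proportion has no interaction, the rule as written is met in 1 - (1 - 0.0916) × 0.95 = 13.7% in the motive-only case and 81% at f = 0.1. The extra openings are false-positive proportion interactions, which say nothing about labelling.

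**7. Selection (motive-only case).** Among trials that meet the precondition, the mean of a × b2 moves only from -0.042 to -0.044. The mean total interaction moves from -0.042 to about -0.152. The apparent mediated share is then about 0.044/0.152 = 29%, where the true share is 100%.

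**The case against.** The strongest reply is that both statements of the hypothesis presuppose a differential effect, so explaining it only after it has been shown is a coherent prespecified sequence that limits the number of tests. That is a legitimate preference. It does not settle the matter, because a non-significant result from a test with 9% to 80% power does not show that moderation is absent, and because Section 7.8 states its power as if the sequence did not exist.

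The reply does rule out several stronger readings that a reader might infer:
- *That the plan's own correlations imply 9%.* They do not. Section 7.8 gives one overall r = -0.25, for kcal ordered in a fast-food task, neither split by labelling nor measured on mean ED. The 9% also needs a slope change of 0.25 and no direct interaction. At the plan's own f = 0.1 the figure is about 80%.
- *That 0.0425 is the most the motive route can produce.* Nothing caps the slope change at 0.25, and two motives are named.
- *That selection inflates the mediation estimate.* It barely moves a × b2; it inflates the total.
- *That the secondary objective gets no answer at all.* The motive scores and their correlations with education are reported regardless, which addresses the first half of the Section 2 hypothesis.

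**Conclusion.** The point holds as a mismatch between the precondition in Section 7.7 and the power statement in Section 7.8. Given a = 0.17 and a slope change of 0.25, the 0.8 power implied for the mediation is not delivered at either significance level for any total interaction up to the planned f = 0.1. Even at that planned value, about one trial in five leaves the moderated mediation untested. The claim that it would *usually* go untested is supported only when the motives are the main route; across the scenarios examined, the chance of meeting the labelling precondition runs from about 9% to 80%. A secondary harm is that the mediated share is understated in the trials that pass. The results rest on the two assumed quantities above and on joint significance in place of the bootstrap. This concerns a secondary objective and is cheap to correct, so the change should be made but does not threaten the primary analysis.

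**What to change.** In Section 7.7, run the labelling moderated mediation for both motives whatever the result of the interaction test, with 99% bootstrap intervals to match the 0.01 level that Section 7 sets for secondary analyses. Where the total interaction is not significant, describe any motive finding as *without a detectable total moderation by education*. The proportion model may stay conditional, since equal effects across SEP are predicted there. Alternatively, because the secondary objective names both interventions, it may be run unconditionally and labelled exploratory. At minimum, if the precondition is kept, restate the mediation power in Section 7.8 as conditional on it, with the assumed slope change and direct interaction written out.

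The cost is one sentence and one extra run per motive on data already collected. The downside is two more secondary tests at the 1% level in trials where the precondition would not have been met.

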### Analyses of secondary outcomes

For descriptive purposes we will code each participant product selection based on the food categories outlined in the shopping list and repeat the primary analysis strategy on each of the 10 food categories individually.

To further investigate the effect of the interventions and level of education, we will repeat the primary analysis strategy with the following dependent variables:

- on total energy of the foods purchased;
- on energy from total sugar;
- on energy from SFA;
- on salt content;

- on proportion of lower ED foods in the basket of foods purchased;
- on cost of the foods purchased.

We will also repeat the primary analysis including the interaction between labelling and proportion in the model.

#### Debriefing questionnaire

We will explore whether the shopping list was valid and the extent to which participants reported being influenced by calorie content when making food choices. Responses to the debriefing questionnaire will be analysed.

- We will report the distribution of responses for *validity* and *kcal influence* (mean, SD, median, quartiles Q1 and Q3) in the overall sample.
- Two ANCOVAs will be run (as in primary analysis) to test the effect of *labelling*, *proportion* and *level of education* on (a) *validity* and (b) *kcal influence* to investigate whether the responses differ across conditions and SEP.

For the labelling conditions only, we will report the percentage of participants who know what the “healthier choice” badge means, i.e., who tick the answer “Fewer calories per gram option”.

#### **7.8. Sample size**

##### To observe differences between the intervention groups and interaction with SEP

In a previous study (n=1,088) using the online supermarket platform, two types of nutritional interventions targeting a reduction of saturated fat (SFA) were compared: 1/ altering the default order of products in ascending order of SFA content 2/ offering explicit swaps with lower SFA [28]. This study showed a large main effect (f=0.42) of altering the default order: -4.78% (95%IC: -5.43 to -4.12) of energy from SFA; and a small-to-medium main effect (f=0.12) of offering swaps: -1.48% (95%IC: -2.19 to -0.76) of energy from SFA. Regarding ED reduction, this study showed a small-to-medium main effect (f=0.14) of altering the default order: -5.16 (95%IC: -7.3 to -3.02); and no significant main effect (f=0.04) of offering swaps -1.5 (95% IC: -3.65 to 0.67).

Based on these previous results, we will power our analyses to detect small main effects (f=0.1) of the *labelling* and *increased proportion* interventions. In an ANCOVA including four groups (*control*, *labelling*, *increased proportion*, *increased proportion & labelling*) and one covariate (*level of education*), to detect a main effect of *labelling* or *increased proportion* we will require a sample size of 788 participants (197 per group) for 80% power at  $\alpha = 0.05$  (GPower 3.1).

A sample size of 788 participants will allow to detect small interaction effects (f=0.1) of *labelling* or *increased proportion* with *level of education* in an ANCOVA including four groups (*control*, *labelling*, *increased proportion*, *increased proportion & labelling*) and one covariate (*level of education*) for 80% power at  $\alpha = 0.05$  (GPower 3.1).

##### To observe a mediated effect of SEP through health and weight control motives

Based on existing literature we hypothesise that the relationship between SEP and food choice motives will be small-to-medium in size [38]. Moreover, in a previous trial we ran using a virtual fast food restaurant ([osf.io/ajcr6](https://osf.io/ajcr6)), we found a small-to-medium correlation between level of education and healthiness motivation ( $r=0.17$ ) as well as small-to-medium correlation between healthiness motivation and kcal ordered ( $r=-0.25$ ). Empirical estimates of sample sizes needed for 0.8 power in mediation analyses indicate that samples of  $\approx 380$  are sufficient to detect mediation through pathways that are small and small-to-moderate in statistical size using bias-corrected bootstrap tests

[39]. Thus, a sample of 788 participants (i.e., 394 per *labelling* or *proportion* condition) allow for adequate power in our planned moderated mediation analysis.

We will recruit a sample of 1,000 participants (= participants who completed the entire study) to account for potential data loss due to incorrect answers, technical problems, failed attention checks, no compliance with the shopping task (up to ~20%) resulting in a minimum sample of 788 participants for our primary analyses.

## APPENDIX A: AUDIENCE (PROLIFIC WEBSITE)

### 1. Age

- 18 years old or over

### 2. Current country of residence

- UK

### 3. Fluent language

- English

### 4. Diet restriction

- None

### 5. Gender

**50% of participants**

- Male

**50% of participants**

- Female

### 6. Students

**96.5% of participants**

- No

**3.5% of participants**

- Yes

### 7. Highest education level

**60% of participants**

- No formal qualifications
- Secondary education (e.g. GED/GCSE)
- High school diploma/A-levels

**40% of participants**

- Technical/community college
- Undergraduate degree (BA, BS, other)
- Graduate degree (MA, MSc, MPhil, other)
- Doctoral degree (PhD, MD, other)

### 8. Are you the main (or shared) grocery shopper for the food that your household eats?

- Yes

**APPENDIX B: RECRUITMENT TEXT**

*“This is a study examining food purchases when shopping online. You will do some online grocery shopping on an experimental supermarket website and fill some questionnaires in about yourself. Please read the instructions carefully and answer the questions as accurately as possible. Failure to comply with the instructions may result in your submission being rejected. Please click on the start button to proceed. Overall the study will take no more than 25 minutes.”*

## APPENDIX E: BASELINE QUESTIONNAIRE

### Eligibility screening:

- **Are you a fluent English speaker?**
  - Yes
  - No → screened out
  
- **Do you currently reside in the UK?**
  - Yes
  - No → screened out
  
- **Do you have any dietary restrictions?**
  - Vegetarian → screened out
  - Vegan → screened out
  - Gluten-free → screened out
  - Sugar-free → screened out
  - Dairy/lactose-free → screened out
  - Food allergy (e.g. milk, eggs, nut, wheat, fish, etc.) → screened out
  - None
  - Other → screened out
  
- **Are you the main (or shared) grocery shopper for the food that your household eats?**
  - Yes
  - No → screened out

### Questionnaire:

#### 1. Gender

- Male
- Female
- Other

#### 2. Age

- \_\_ (free text; range of 18-99)

#### 3. Ethnicity

- White
- Black
- Asian
- Mixed
- Other

#### 4. What is your current employment status?

- Full or part-time
- Student
- Retired
- Temporary or permanently sick or disabled
- Looking after home/family
- Other unemployed

**5. What is your highest educational qualification? If you are a student please select the diploma being studied for.**

- No formal qualifications
- 1–3 GCSEs or equivalent
- 4+ GCSEs or equivalent
- A level or equivalent
- Certificate of higher education (CertHE) or equivalent
- Diploma of higher education (DipHE) or equivalent
- Bachelor or equivalent
- Master’s degree or equivalent
- Doctorate or equivalent

**6. After leaving school (i.e. at 16 years old), how many further years of higher education (i.e. a formal course) did you study for?**

*Examples:*

*If you left school and did not go on to study further in higher education, your answer would be 0.*

*If you left school and then studied for two years for A levels, your answer would be 2.*

*If you completed A levels over two years and then also studied for a three year undergraduate degree, your answer would be 5.*

\_\_ (free text)

**7. What is your annual after tax household income, including all earners in your household, in GBP (to the nearest £1000)?**

£\_\_\_\_ (free text; range 0-999,999)

**8. How many people live at your house, including you?**

\_\_ adult(s) or child(ren) aged 14 and over (free text; range of 1-20)

\_\_ child(ren) aged under 14 (free text; range of 1-20)

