### 7.2. Participant's characteristics

A table will present the baseline characteristics by condition group and overall. The table will include gender, age, ethnic group, proportion of students, highest educational qualification, years in higher education, equivalised household income, subjective socioeconomic position, BMI, dieting status, grocery shopping in supermarkets frequency, grocery shopping online frequency. Continuous variables will be summarised using means and standard deviations. Categorical variables will be summarised using counts and percentages.

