#### Independent variables

##### **SEP**

#### **Level of education**

- **Highest educational qualification** will be coded from 1 to 9: 1 = No formal qualifications; 2 = 1–3 GCSEs; 3 = 4+ GCSEs; 4 = A level; 5 = Certificate of higher education (CertHE); 6 = Diploma of higher education (DipHE); 7 = Bachelor; 8 = Master’s degree; 9 = Doctorate, and as a binary variable as *lower* (values: 1, 2, 3, 4) or *higher* (values: 5, 6, 7, 8, 9).
- **Years in higher education**, as a continuous variable
- **Level of education (composite score):** In order to account for years in higher education and highest education qualification when characterising each participants’ education level, we will z-score the two variables and create an average of the two to form a composite score called ‘*level of education*’.

**Equivalent household disposable income:** The OECD-modified equivalence scale will be used to adjust household income, taking into account household size and composition [24]. Equivalent income will be calculated by dividing the after tax household income by the sum of the equivalence value of all the household members: first adult = 1, additional adult or child aged 14 and over = 0.5, child aged 0-13 = 0.3.

**Subjective SEP:** The measure of the Subjective Social Status using the MacArthur Scale will be coded from 1 to 10.

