#### 7.4. Missing data

We do not anticipate missing data for analysis of the primary outcome for the population because ED is calculated based on the food database embedded in the online supermarket platform. We do not anticipate missing data either for the dependant variables because the questionnaires will not allow missing answers. Data from participants who start but not finish the study will not be included. Any *a posteriori* withdrawal will be reported and reasons for withdrawal will be documented (e.g., incorrect answers, technical problems).

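### Appendix E, question 8 does not accept 0 for children under 14; if the live form enforces this, equivalised income is understated for households without such a child

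*Combined protocol and SAP*

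**What the plan says.** Appendix E, question 8 asks for household size in two fields. The first is "adult(s) or child(ren) aged 14 and over (free text; range of 1-20" and the second is "child(ren) aged under 14 (free text; range of 1-20". Both fields have the same lower limit of 1.

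Section 7.3 turns the answers into an equivalised income: "Equivalent income will be calculated by dividing the after tax household income by the sum of the equivalence value of all the household members". The weights are "first adult = 1, additional adult or child aged 14 and over = 0.5, child aged 0-13 = 0.3".

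Section 7.4 does not expect missing questionnaire data, on the ground that "the questionnaires will not allow missing answers".

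Section 5.2 lists equivalised income among the SEP measures. Section 7.2 puts it in the baseline table, by condition and overall, in the run "equivalised household income, subjective socioeconomic position".

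**The concern.** A lower limit of 1 suits the first field, because the respondent is always counted there. It does not suit the second, where 0 is a natural answer. Neither the eligibility criteria (Sections 4.2 and 4.3) nor the screening questions in Appendix E require a participant to live with a child. No section offers a 'none' option, a skip rule, or a rule that a blank counts as 0. Elsewhere the form allows zero where zero is possible: the income field in question 7 reads "free text; range 0-999,999", and the guidance to question 6 gives 0 as a possible answer.

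Two things are at stake. First, each false child adds 0.3 to the income divisor, so equivalised income is biased downward for one type of household and not for the other. In a trial about SEP, the baseline table tells readers whom the results describe. Second, the error could not be undone afterwards. A recorded 1 might be a real child or a forced entry, and nothing else in the questionnaire asks about children.

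**Working it through.** The plan gives no equivalised income value and no household mix, so there is no stated figure to reproduce. The check applies the plan's own formula with and without one false child.

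**Inputs**
- Weights (Section 7.3): 1 for the first adult, 0.5 for each further member aged 14 and over, 0.3 for each child aged 0-13.
- Smallest entry allowed in the under-14 field (Appendix E, question 8): 1.
- True number of children under 14 in the affected households: 0.

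**Formulas**, with *k* members aged 14 and over:
- true divisor: T = 1 + 0.5 × (k − 1)
- divisor with one false child: W = T + 0.3
- proportional understatement: 1 − (income/W)/(income/T) = 1 − T/W

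Income cancels, so the percentage is the same at every income.

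| k | T | W | 1 − T/W | Equivalised income at an assumed £30,000: true → recorded |
|---|---|---|---|---|
| 1 | 1.0 | 1.3 | 23.1% | £30,000 → £23,077 |
| 2 | 1.5 | 1.8 | 16.7% | £20,000 → £16,667 |
| 3 | 2.0 | 2.3 | 13.0% | £15,000 → £13,043 |
| 4 | 2.5 | 2.8 | 10.7% | £12,000 → £10,714 |

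The £30,000 is illustrative only; the percentages do not depend on it.

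**Effect on comparisons between households.** A household that does have a child under 14 can report correctly and has no error. A person living alone on £30,000 who enters 1 is recorded at 30,000/1.3 = £23,077. A lone adult with one real child under 14 and the same income is also recorded at £23,077, and for that household the figure is right. The two become indistinguishable, although the true value for the first is £30,000.

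**Effect on the table row.** The documents do not give the share of participants with no child under 14. If that share were 0, the overall mean would be unaffected. If every participant lived alone with no child and entered 1, the mean would be 23.1% too low. With entries of 1, the actual understatement lies between these limits.

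**Where the variable is used.** In Section 7, equivalised income has a planned use only in the Section 7.2 table. Section 7.5 uses the composite level of education. Section 7.6 substitutes years in higher education and binary qualification. The mediation, secondary-outcome and debriefing analyses in Section 7.7 use level of education. The sample size in Section 7.8 does not involve income.

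**The case against.** The strongest reply is that the plan does not establish compulsion field by field. The Section 7.4 sentence is a general expectation about missing data, attached to what the plan calls the dependent variables; household composition is not one of them. The same questionnaire also has fields that evidently may stay blank: weight can be given in kilograms or in stones and pounds, height in centimetres or in feet and inches, and Section 7.3 converts the imperial entries. Question 8 is likewise one question with two fields, so a form that demands an answer per question might accept a blank second field. The identical ranges on adjacent lines also suggest a drafting slip that may never have been live.

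This stands, and it limits the point. A reader might infer that every household with no child under 14 is bound to report one that does not exist. The documents do not support that, because it depends on how the live form was set and they do not show the setting.

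Two further objections also stand. A reader might infer a threat to the trial's main result or to the balance between arms. No hypothesis test uses income, and the study flow in Section 6 places the baseline questionnaire before randomisation, so any error arises independently of condition. Drop-out at this question is possible, and only completers are analysed (Section 7.1), but nothing in the documents shows that it would happen. If it did, it would alter who enters the trial, not the randomised comparison.

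The reply does not remove the defect. The printed range still excludes the true value, and no text says how a blank would be handled.

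**Conclusion.** The point holds as a conditional one. As printed, question 8 bars a truthful 0 for any household with no child under 14, including households whose only children are 14 or over. If the live form enforces both the range and compulsory answers, equivalised income in those households is understated by 23.1%, 16.7% or 13.0% for one, two or three members aged 14 and over, assuming the participant enters the minimum of 1. A larger false entry would make it worse.

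The consequence is limited to one descriptive row and to the description of the sample's SEP. The correction is worth making before data collection because it costs almost nothing then and the error cannot be separated out later. A reader might conclude that the variable should be dropped outright. That goes too far, since it is a pre-specified baseline characteristic and the fault may exist only on paper.

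**What to change.** Change the under-14 range in Appendix E, question 8 to 0-20, and confirm by test entry that the live form accepts 0. This is one field setting and has no drawback.

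If data have already been collected, check the live setting and the recorded values first:
- If zeros or blanks were accepted, treat blanks in this field as 0, say so in the report, and present equivalised income as planned.
- Only if 1-20 was enforced, flag equivalised income as unreliable in the baseline table and state the direction of the error (downward, for households with no child under 14).

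Neither route changes the primary, sensitivity or mediation analyses, or the sample size.
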